8.3 Definition of an AE

An AE is any untoward medical occurrence in a clinical investigation patient administered a product or medical device, unless the event is captured in the study endpoint, as defined below; the event need not necessarily have a causal relationship with the treatment or usage.

An event would be considered as adequately captured in the study endpoint if it is accurately and fully represented by a protocol-defined reason for clinical failure (other than mortality) or relapse. Such an event should not be reported as an adverse event unless it is a serious adverse event as defined in this protocol.

Events represented by the study endpoints include all of the following:

- Symptoms of uUTI have not resolved from Baseline to such an extent that new antibiotics are not needed for the infection under study
- Development of new uUTI symptoms not present at Baseline
- Follow up urine cultures do not reveal eradication of causative uropathogen

Except for circumstances as defined above, examples of AEs include but are not limited to:

- Clinically significant symptoms and signs;
- Hypersensitivity;
- Progression/worsening of underlying disease.

Additionally, they may include the signs or symptoms resulting from:

Clinical Trial Protocol: IT-004-401

- Drug overdose;
- Drug withdrawal;
- Drug abuse;
- Drug misuse;
- Drug interactions;
- Drug dependency;
- Exposure during Pregnancy.

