5 DEFINITION OF OUTCOME MEASURES

5.1 Primary Efficacy Outcome Measure

The primary efficacy outcome is overall response assessed on Day 12 (+/- 1 day) in the m-MITT using the definitions listed below.

A patient will be programmatically defined as a responder based on the following:

- The patient is alive;
- The patient has received no rescue therapy for uUTI (if an antibiotic active against the urinary tract pathogen is given for other reasons, then the patient will be considered indeterminate, and analyzed as a non-responder);
- The patient has resolution of the symptoms of uUTI present at trial entry and no new uUTI symptoms, on Day 12 (+/- 1 day);
- Urine culture taken on Day 12 (+/- 1 day) demonstrates <10³ CFU/mL of the baseline uropathogen;

A patient will be defined as a non-responder if at least one of the following criteria is met:

- The patient has died:
- The patient has received rescue therapy for uUTI (If an antibiotic active against the urinary tract pathogen is given for other reasons, then the patient will be considered indeterminate, and analyzed as a non-responder for uUTI);
- The patient has no resolution or worsening of the symptoms of uUTI present at trial entry and/or with new uUTI symptoms;
- Urine culture taken demonstrates $\geq 10^3$ CFU/mL of the baseline uropathogen;

All other patients will be considered indeterminate, including those with missing data needed to determine if the patient is a responder or non-responder. For example, if either urine culture or uUTI symptoms are not completed, the patient will be considered an indeterminate.

For the ITT and m-MITT populations, the proportion of ITT or m-MITT patients with a responder is defined using the following formula:

Number of responders

Number of responders + Number of non-responders + Number of indeterminates

By definition, patients in the CE and ME populations must have sufficient information for determination of efficacy response. Thus, the proportion of CE and ME patients is defined using the following formula:

Number of responders + Number of non-responders

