5.1.1 Additional Analysis of the Primary Efficacy Outcome Measure

In addition to the primary efficacy outcome measure, following sensitivity analyses will be performed on Day 12 (+/- 1 day) in the m-MITT population,

- Sensitivity Analysis 1: Will follow the same definition of primary outcome measure defined in section 5.1 except, urgency is excluded and considering all other symptoms (in Appendix 2) are resolved and no new uUTI symptoms.
- Sensitivity Analysis 2: Will follow the same definition of primary outcome measure defined in section 5.1 except, frequency is excluded and considering all other symptoms (in Appendix 2) are resolved and no new uUTI symptoms.
- Sensitivity Analysis 3: Will follow the same definition of primary outcome measure defined in section 5.1 except, improvement of symptoms (instead of resolution, in Appendix 2) from baseline and no worse than mild from baseline and no new uUTI symptoms are considered.
- Sensitivity Analysis 4: Will follow the same definition of primary outcome measure defined in section 5.1 except, improvement of symptoms (instead of resolution, in Appendix 2) from baseline and no new uUTI symptoms are considered.
- Sensitivity Analysis 5: Will follow the same definition of primary outcome measure defined in section 5.1 except, urgency and frequency are improved and no worse than mild from baseline and all other symptoms (in Appendix 2) are resolved and no new uUTI symptoms are considered.
- Sensitivity Analysis 6: Will follow the same definition of primary outcome measure defined in section 5.1 except, investigator response will be used instead of symptoms filled in by patient (from patient dairy).

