5.3 Additional Efficacy Outcomes Measures

Microbiologic response

Microbiologic response is assessed on Day 3 or 4 (+1 day) EOT and Day 12 (+/- 1 day) TOC in the ITT, m-MITT, CE-EOT, CE-TOC, ME-EOT and ME-TOC populations.

Microbiological	Definition
response	
Eradication	A urine culture taken at baseline and compared with the culture
	from the Day 3 (+1 day) (EOT) visit or Day 12 (+/- 1 day)
	(TOC) visit showed that the urine culture obtained at the
	relevant visit demonstrated <10 ³ CFU/mL of the original
	uropathogen.
Persistence	Uropathogen present at baseline grew at ≥10 ³ CFU/mL at the
	time-point of analysis, i.e. EOT or TOC.
Indeterminate	Patient was lost to follow-up or an assessment was not
	undertaken such that no urine culture was obtained (or culture
	results could not be interpreted for any reason) at either the
	EOT or the TOC visit.

• Clinical response:

Clinical response (done programmatically) will use the definitions below to document response at Day 3 or Day 4 (+ 1 day) (EOT), Day 12 (+/- 1 day) (TOC) and Day 21 in the ITT, m-MITT, CE-EOT, CE-TOC, ME-EOT and ME-TOC populations.

Clinical response	Definition
Clinical cure	All pre-therapy signs and symptoms of the index infection had resolved such that no additional antibiotics were required
Clinical failure	Patients who met any one of the criteria below were considered as failure:
	Death related to uUTI prior to Day 3 or Day 12 or Day 21 respectively
	No apparent response to treatment; persistence or progression of most or all pre-therapy signs and symptoms or use of additional antibiotics for the current infection
	Patient previously met criteria for failure and received rescue antibiotics
Indeterminate	Study data were not available for evaluation of efficacy for any reason, including:
	Patient lost to follow-up or assessment not undertaken such that a determination of clinical response could not be made at either the EOT or TOC visit
	Death prior to Day 3 or Day 12 or Day 21, respectively, where uUTI was clearly noncontributory

In addition to the clinical response above, following sensitivity analyses will be performed on Day 12 (+/- 1 day) in the m-MITT population,

- Sensitivity Analysis 1: Will follow the same definition of clinical response defined in section 5.3 except, urgency is excluded and considering all other symptoms are resolved and no new uUTI symptoms.

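### Programmatic clinical cure in SAP 5.3 has no new-symptom condition, unlike the primary endpoint and the five sensitivity analyses built on it

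*SAP*

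**What the plan says.** SAP 5.3 states: "Clinical response (done programmatically) will use the definitions below to document" response at EOT, TOC and Day 21. Cure is "All pre-therapy signs and symptoms of the index infection had resolved such that no additional antibiotics were required". The symptom and antibiotic limb of failure is no apparent response, with "persistence or progression of most or all pre-therapy signs and symptoms or use of additional antibiotics for the current infection". The other limbs are death related to uUTI, and earlier failure with rescue antibiotics. New symptoms appear in neither row.

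SAP 5.1 differs. A responder must have her entry symptoms resolved and no new ones. One of the criteria sufficient for non-response is "The patient has no resolution or worsening of the symptoms of uUTI present at trial entry and/or with new uUTI symptoms".

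The five clinical-response sensitivity analyses in SAP 5.3 (Day 12, m-MITT) each say that they follow the 5.3 definition with one exception. All five then carry the new-symptom condition. The first, for example, reads "urgency is excluded and considering all other symptoms are resolved and no new uUTI symptoms".

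The investigator definition (Protocol 7.2.3, SAP 5.3) has the same cure wording and the same silence. Sensitivity Analysis 6 of the primary endpoint (SAP 5.1.1) relies on it: "investigator response will be used instead of symptoms filled in by patient". SAP Section 8 records another edit to the clinical-response rule but not this difference.

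**The concern.** Because a program assigns the category, the written rule decides it and no clinician can supply a condition that the text omits. Women who fail the symptom part of the primary endpoint only through a new symptom would be tabulated as clinical cures. That affects clinical response at EOT, TOC and Day 21 in the ITT, m-MITT, CE and ME populations, and the EOT and TOC tables by pathogen and by ESBL status.

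The sensitivity analyses are also not nested in their base case. A reader will take the gap between base and sensitivity result as the effect of relaxing the urgency, frequency or resolution rule. Part of that gap may instead come from a new-symptom condition present on one side only.

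**Working it through.** No figure in the plan depends on this definition, so there is none to reproduce. The check applies the written rules.

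**Step 1: one woman under each rule.** Protocol 4.1 requires two of five symptoms at entry. Suppose burning and frequency at entry; at Day 12 both are gone, suprapubic pain is present, and no additional antibiotic was taken.

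| Rule | New-symptom condition | Result |
|---|---|---|
| Programmatic clinical response (SAP 5.3) | none | cure |
| Primary endpoint, symptom criterion (SAP 5.1) | yes | non-responder |
| Clinical Sensitivity Analyses 1 to 5 (SAP 5.3) | yes | not a cure |
| Investigator response (Protocol 7.2.3, SAP 5.3) | none | cure as worded |

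**Step 2: how wide the gap in the rule is.** Take the five entry symptoms as present or absent, with k present at baseline.

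- Eligible baseline patterns (k = 2 to 5): 10 + 10 + 5 + 1 = 26.
- Literal cure: the k baseline symptoms are absent at Day 12 and the other 5 − k are free, which gives 2^(5−k) Day 12 patterns each. Total: 10×8 + 10×4 + 5×2 + 1×1 = 131.
- Primary symptom criterion: all five absent, one Day 12 pattern each, so 26.
- Cure by SAP 5.3 but symptom non-responder by SAP 5.1: 131 − 26 = 105.
- All 105 fail Sensitivity Analyses 3 to 5. For Analysis 1, if urgency is also ignored as a new symptom, 6 + 4 + 1 = 11 patterns have new urgency only, so 105 − 11 = 94 fail. Analysis 2 gives the same count for frequency.

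A new symptom is possible in 25 of the 26 baseline patterns (all except the one with all five present). These are counts of possible patterns, not expected frequencies.

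**Step 3: effect on a sensitivity comparison.** Among N women, consider those with no additional antibiotic. Let a = resolved with no new symptom, b = resolved with a new symptom, and c = improved but not fully resolved with no new symptom. For Sensitivity Analysis 4:

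- base case as written: (a + b)/N
- sensitivity analysis: (a + c)/N
- difference: (c − b)/N

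With the condition in the base case, the difference would be (a + c)/N − a/N = c/N, which is the effect the analysis is meant to show. As written it is short by b/N.

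**Step 4: size.** The expected m-MITT is 250 − 50 = 200 (Protocol 9.1, SAP 6.1). If a share q of these women falls in group b, 200q extra women are scored as cures and the rate rises by q. The documents give no q. Assuming 1% to 10%, for scale only:

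| Assumed q | Extra cures of 200 | Rise in cure rate |
|---|---|---|
| 1% | 2 | 1 point |
| 5% | 10 | 5 points |
| 10% | 20 | 10 points |

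**The case against.** The strongest reply is that this is a drafting slip in an additional descriptive outcome. The primary endpoint has its own new-symptom rule, there is no hypothesis test (SAP 7.6), and the sample size does not depend on clinical cure. PSAQ results are tabulated at EOT and TOC, and reasons for non-response are summarised for most endpoints, so these women need not be hidden. The sensitivity analyses copy the pattern of those for the primary endpoint, where the base case does contain the condition, so the authors may have believed it was in 5.3 as well.

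All of this limits the consequence. It does not remove the mismatch: if the authors meant the condition to apply, the text that will be programmed does not say so.

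Four stronger readings are tempting, and the documents do not support them.

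- *New symptoms vanish from reporting, being neither a failure nor an AE.* Protocol 8.3 does list "Development of new uUTI symptoms not present at Baseline" among endpoint events that are not reported as AEs unless serious. But the same list includes non-eradication on culture, so it tracks the composite overall response, where new symptoms do count.
- *A relaxed analysis will give a lower cure rate than the base case.* By Step 3, Sensitivity Analysis 4 does so only if b exceeds c, and nothing in the documents bears on that.
- *Clinical cure is overstated by a known amount.* No frequency is given.
- *With the fix, cure plus eradication would equal overall response.* An active antibiotic given for another reason makes overall response indeterminate, while clinical failure covers only antibiotics for the current infection.

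**Conclusion.** The point holds as an internal inconsistency with a practical effect. Followed literally, the SAP 5.3 rule scores as cured any woman whose baseline symptoms resolved, who has a new uUTI symptom and who took no additional antibiotic. The same woman fails the primary symptom criterion. The five clinical sensitivity analyses differ from their base case in two respects, so their differences from it cannot be read as the effect of the relaxed rule.

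The effect is 1 percentage point of clinical cure for each 1% of such women, at an unknown frequency. The primary result does not change.

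The conclusion assumes that the program follows the written text. The pattern count also treats the five symptoms separately. The newer PSAQ merges frequency and urgency (Protocol Appendix 3, SAP Appendix 2), so on that form new urgency in a woman with baseline frequency cannot be recognised as new.

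**What to change.** 1. In SAP 5.3, add absence of new uUTI symptoms to programmatic clinical cure, and add new uUTI symptoms to clinical failure, at EOT and TOC, taken from the PSAQ. Change both rows: if only cure changes, these women are neither cure nor failure, and membership of the CE population requires one or the other.
2. State what applies at Day 21. SAP 5.3 reports clinical response there, but the schedule has no PSAQ at that visit, only a telephone call about symptom resolution (Protocol 6.3.2 and Appendix 1).
3. Leave Sensitivity Analysis 6 of the primary endpoint as investigator response. Add a note that the investigator definition has no new-symptom condition, so its difference from the primary result reflects both the assessor and the rule. Adding a PSAQ check would create a hybrid and would not isolate the assessor.
4. Record the changes in SAP Section 8.

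The cost is SAP wording and a few lines of code. EOT and TOC need no new data. The downside is a slightly lower clinical cure rate.

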5.4 Safety Outcome Measures

The safety parameters include adverse events (AEs). No additional laboratory testing will be performed beyond routine urine testing for uUTI. AEs will be coded using the Medical Dictionary of Regulatory Activities (MedDRA) Version 21.0 to the System Organ Class and Preferred Term levels.

6 STATISTICAL METHODS

6.1 Sample Size

The study is designed to determine the clinical and microbiologic efficacy of ciprofloxacin for adult female patients with uUTI, due to either a ciprofloxacin susceptible or non-susceptible organism. Two-hundred fifty (250) symptomatic patients will be enrolled with the expectation that there will be no screen failures. Of the 250 enrolled patients, we expect 50 will not have a positive urine culture for $\geq 10^5$ CFU/mL of a uropathogen at baseline. Of the 250 enrolled patients, we expect 40 will have a uUTI due to a ciprofloxacin non-susceptible organism.

Patients who withdraw prior to initial dose, will be replaced to ensure a total of 250 patients

will receive at least a single-dose of ciprofloxacin.

6.2 Randomization

No randomization performed. Approximately 250 female patients with uUTI will be administered oral ciprofloxacin twice daily for 3 days.

A patient will be eligible for the study once it has been determined that she meets all inclusion criteria and has none of the exclusion criteria.

6.3 Visit Windows for Efficacy Analysis

No analysis will be performed for any unscheduled visits.

Visit	Window
Baseline	Day -1 or 1, defined as period prior to the administration of the first dose of study drug
Day 3 or Day 4 (EOT)	+1 day
Day 12 (TOC)	± 1 days
Day 21	± 3 days

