6.4 Patient Withdrawal from Treatment or Study

Patients may withdraw from the study or ciprofloxacin at any time at their own request, or they may be withdrawn at any time at the discretion of the Investigator or Iterum Therapeutics for safety, behavioral, or administrative reasons.

If a patient does not return for a scheduled visit, every effort should be made to contact the patient. In any circumstance, every effort should be made to document patient outcome, if possible. If the patient withdraws or is withdrawn from ciprofloxacin treatment, the Investigator should inquire about the reason for withdrawal, request the patient to return for all protocol-specified assessments, if possible, and follow-up with the patient regarding any unresolved AEs through the TOC.

If the patient withdraws from the study, and also withdraws consent for disclosure of future information, no further study-specific evaluations should be performed, and no additional data should be collected. Iterum Therapeutics may retain and continue to use any data collected before such withdrawal of consent.

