4.5 Clinically Evaluable (CE)

Clinically evaluable is defined both at the end of treatment (EOT) and test of cure (TOC) visits.

- All patients who were included in the MITT population and meet the following criteria are clinically evaluable.
 - a) Received a minimum of four doses of ciprofloxacin.
 - b) Had no important protocol deviations that would affect the assessment of efficacy as indicated in the protocol deviation log (see section 7.9). These will be pointed out by clinical team and marked in the CE spreadsheet.
 - c) Had a Clinical response assessment of clinical cure or clinical failure (and not indeterminate) at the EOT or TOC visits (within Protocol visit window), respectively.
 Note: Since the PSAQ does not contain a date completed, the date if lab culture will be used.
 - d) Did not receive any antibiotic therapy with potential activity against any of the baseline uropathogens collected at screening between the time of the baseline culture and the EOT or TOC culture, respectively. This excludes the protocol defined study therapy and patients who were considered clinical failures and required additional antibiotic therapy. Patients with a coinfection with a gram-positive uropathogen resistant to ciprofloxacin are allowed to receive agents with narrow spectrum gram-positive coverage (i.e., such as linezolid or vancomycin).

Note: This rule will be applied through the manual review of CE spreadsheet by the sponsor.

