4.6 Microbiologically Evaluable (ME)

All patients included in both the m-mITT and CE populations at the EOT visit (ME-EOT), and at the TOC visit (ME-TOC) and meet the following criteria are microbiologically

evaluable:

a) Have an appropriately collected urine culture specimen and interpretable urine culture result at the EOT and TOC visits, respectively.

b) Had a microbiologic assessment of eradication or persistence (and not indeterminate) at the EOT or TOC visits, respectively.

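### A woman with a documented positive culture after EOT and no Day 12 culture drops out of ME-TOC, and in some cases CE-TOC, because the SAP ignores unscheduled visits and carries no persistence forward

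*SAP*

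**What the plan says.** **Visits.** Appendix 1 of both documents schedules EOT on Day 3 or 4 (+1 day), TOC on Day 12 (±1 day) and a telephone call around Day 21. Nothing is scheduled between EOT and TOC. On other contacts, SAP 6.3 says: "No analysis will be performed for any unscheduled visits". The protocol has no such exclusion, and SAP section 8 does not list it among the differences from the protocol.

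**Evaluable populations.** For CE, SAP 4.5(c) requires that the woman "Had a Clinical response assessment of clinical cure or clinical failure (and not indeterminate) at the EOT or TOC visits", inside the visit window. A note dates that window by the laboratory culture because the symptom questionnaire carries no date. For ME, SAP 4.6(a) requires an interpretable culture at the visit in question, and 4.6(b) adds: "Had a microbiologic assessment of eradication or persistence (and not indeterminate) at the EOT or TOC visits, respectively".

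**Outcome rules.** SAP 5.3 defines persistence only at EOT or TOC. Programmatic clinical failure is carried forward only for women who received rescue antibiotics, a narrowing that SAP section 8 declares. For overall response, SAP 5.1 says "A patient will be defined as a non-responder if at least one of the following criteria is met", and one criterion is "The patient has received rescue therapy for uUTI". The same section says "All other patients will be considered indeterminate, including those with missing data needed to determine if the patient is a responder or non-responder", with the example that "if either urine culture or uUTI symptoms are not completed, the patient will be considered an indeterminate".

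**Site instruction.** Protocol 6.4, on withdrawal and missed visits, says: "In any circumstance, every effort should be made to document patient outcome, if possible".

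**The concern.** A woman whose infection persists after EOT can be seen before Day 11 only at an unscheduled contact. A culture taken there that grows the baseline uropathogen at or above the persistence threshold is direct evidence of failure. Under the present rules, if no Day 12 culture follows, that result is not used and her microbiologic outcome is handled as missing.

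In CE-TOC and ME-TOC, missing means removed from the denominator. Everyone removed by this route is a known microbiologic failure, so the response and eradication rates in those populations can only move up. In m-MITT the rate does not move. However, the split between non-responder and indeterminate does, and the table of reasons planned in SAP 7.6 would report known persistence as absent data.

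**Working it through.** **Step 1. Trace the rules.** Take a woman with a positive culture at an unscheduled visit after EOT who then misses Day 12.

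| Item | No rescue | Rescue antibiotics given |
|---|---|---|
| Microbiologic response at TOC (SAP 5.3, 6.3, 6.5) | Indeterminate | Indeterminate |
| Clinical response at TOC (SAP 5.3, 6.5) | Indeterminate | Failure, through additional antibiotics |
| Overall response (SAP 5.1) | Indeterminate under the missing-data sentence; non-responder if the undated culture bullet is applied | Non-responder under the rescue bullet; indeterminate under the missing-data sentence |
| CE-TOC (SAP 4.5) | Out, by (c) | Meant to stay: (d) spares rescued failures. But (c) dates the window by a culture she does not have |
| ME-TOC (SAP 4.6) | Out, by (a) and (b) | Out, by (a) and (b) |

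Rescue is visible to the analysis because Protocol 5.4.1 has antibiotics for the primary uUTI recorded in the CRF as medication, not as visit data.

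**Step 2. Primary rate.** SAP 5.1 gives the m-MITT rate as R/(R + N + I), with R responders, N non-responders and I indeterminates. Moving a woman from N to I leaves both numerator and denominator as they were. The change is 0.

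**Step 3. Inputs for size.** Protocol 9.1 and SAP 6.1 give 250 enrolled, 50 expected without a positive baseline culture and 40 expected non-susceptible. No power, precision target or response rate lies behind the 250, so only the subtraction can be reproduced: 250 − 50 = 200 expected culture-positive.

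The rest is assumed: response or eradication p of 50% to 80% when these women are counted as failures; all 200 otherwise evaluable; all 40 non-susceptible cases among them. Let k be the number of women on this route and R = p × n.

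**Step 4. ME-TOC.** Rescue makes no difference here. Shift = R/(n − k) − R/n.

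| n | k | p = 50% | p = 80% | Shift (points) |
|---|---|---|---|---|
| 200 | 2 | 100/198 = 50.5% | 160/198 = 80.8% | 0.5 to 0.8 |
| 200 | 5 | 100/195 = 51.3% | 160/195 = 82.1% | 1.3 to 2.1 |
| 200 | 10 | 100/190 = 52.6% | 160/190 = 84.2% | 2.6 to 4.2 |
| 200 | 20 | 100/180 = 55.6% | 160/180 = 88.9% | 5.6 to 8.9 |
| 40 | 1 | 20/39 = 51.3% | 32/39 = 82.1% | 1.3 to 2.1 |
| 40 | 2 | 20/38 = 52.6% | 32/38 = 84.2% | 2.6 to 4.2 |
| 40 | 4 | 20/36 = 55.6% | 32/36 = 88.9% | 5.6 to 8.9 |

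**Step 5. CE-TOC.** If the rescue rules keep rescued women in, only (1 − f)k leave, where f is the share rescued. With n = 200, p = 70% (R = 140) and k = 10:

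- f = 0: 140/190 = 73.7%, +3.7 points
- f = 0.5: 140/195 = 71.8%, +1.8 points
- f = 0.8: 140/198 = 70.7%, +0.7 points
- f = 1: 140/200 = 70.0%, no shift

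If the dating note in 4.5(c) removes rescued women too, the f = 0 line applies whatever f is. CE is drawn from MITT rather than m-MITT, so its denominator may exceed 200 and the shift would then be smaller.

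**The case against.** The strongest reply is that the plan already catches most early failures. A woman who returns early and is re-treated is a non-responder under 5.1 and a clinical failure under 5.3, and 4.5(d) is written to keep her in CE. That stands for the intent. A reader might infer from 6.3 that every sign of early failure is discarded; the documents do not support this, because rescue is recorded as medication and still counts. What remains is the dating note in 4.5(c), and the loss from ME-TOC, which rescue does not prevent.

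Second, 6.3 is not the only cause. SAP 4.6(a) alone removes from ME-TOC any woman without a TOC culture. This stands, and it means that rewording 6.3 by itself would not restore her.

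Third, 5.1 can be read as already scoring her a non-responder: one criterion is enough, and its culture bullet names no day. That reading is available, but it collides with 6.3 and with the missing-data sentence in 5.1, so two programmers could reach different answers. It also does not return her to CE-TOC or ME-TOC.

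Fourth, limiting clinical carry-forward to rescued women is a choice declared in SAP section 8, and the endpoint is status at Day 12. This stands for symptoms alone. A rate with early failures added back rests on a carry-forward convention and should not be called the true rate.

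Fifth, the study is descriptive, the affected rates are supportive, and SAP 7.6 will show reasons for indeterminate for most endpoints. This limits the consequence without removing the bias. Nor is the non-susceptible row above an explicitly planned ME-TOC result: Protocol 9.5.1.1 attaches the susceptibility split to the primary outcome, and SAP 5.3 plans ME results by pathogen and by ESBL status.

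**Conclusion.** The point holds for the supportive populations. A woman with documented persistence after EOT and no Day 12 culture leaves ME-TOC with or without rescue. She leaves CE-TOC if she misses Day 12 unrescued, and may leave it if rescued. The bias in CE-TOC and ME-TOC is upward.

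Two stronger conclusions are not supported. The primary m-MITT response rate is not inflated; only its non-responder/indeterminate split and the table of reasons are affected. And no particular size can be claimed. The shifts shown, from 0.5 to 8.9 points in ME-TOC, depend entirely on the assumed k and p. The documents give no expected number of such women and do not show that unscheduled cultures are entered in the CRF. SAP 7.3 plans a listing of post-baseline isolates but does not say whether unscheduled ones are included.

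This is a low-cost improvement worth making. It does not threaten the primary result.

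**What to change.** 1. **SAP 6.3.** Add one exception: a recorded unscheduled culture after EOT with ≥10^3 CFU/mL of the baseline uropathogen is carried forward to TOC as persistence and non-response when rescue was received or no TOC culture follows.
2. **SAP 4.5(c) and 4.6(a) and (b).** Add matching exceptions so that documented failures, including rescued women with no TOC culture, stay in CE-TOC and ME-TOC if they meet the remaining criteria. Without this step, step 1 does not change ME-TOC.
3. **SAP 5.1.** State that the non-responder rule takes precedence over the missing-data sentence, and reconcile 5.1, 5.3 and 6.3.
4. **Symptoms alone.** Carrying forward symptoms in unrescued women would reverse the choice declared in SAP section 8. It should be a sensitivity analysis at most.
5. **Data check.** Confirm whether unscheduled cultures are in the CRF, and report how many women the rule affects. List the change in SAP section 8.

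The cost is a few sentences, minor programming, and CE and ME rates that may be slightly less favourable. No extra visit or specimen is needed. If unscheduled cultures were not captured, the rule has nothing to act on and the report should say so.
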